The goal of this aim is to assess changes in delay discounting for children and parents assigned to FBT versus UC and to assess the relationship between those changes and weight control. We hypothesize that FBT will be associated with reductions in delay discounting for children and parents compared with UC, and that the degree of change in delay discounting will be related to success in weight control. *All analyses in this aim will be performed separately for the index child and the index parent (DSMB approved protocol addenda, 11.2.18).* Delay discounting will be measured using the k-value detailed by Johnson and Bickel.⁷⁵ These parameters will be measured at baseline, 12, and 24 months. One set of analyses in this aim will involve random coefficient models that compare the pattern of change in the k value in the UC group with corresponding changes in the FBT group. We will also use bivariate linear mixed models implemented by PROC MIXED in SAS⁷⁶ to evaluate the association between changing k-values and changes in weight.

D. Analysis of Secondary Aim 4 (DSMB approved protocol addenda, 11.2.18).

The goal of this aim is to examine participant level baseline predictors of outcomes, with the measures of interest being parental inconsistency and environmental enrichment. We hypothesize that FBT, as compared to UC, will benefit families with higher parental inconsistency and less enriched environments. Parental inconsistency will be measured using a validated parenting style inventory⁷⁷ while environmental enrichment will be evaluated using questions from the HOME⁷⁸ scale developed by Rosenberg et al⁷⁹ and the Land Use Mix-Diversity subscale from the Neighborhood Environment Walkability Scale (NEWS)⁸⁰ that we have employed previously⁸¹ in a pediatric weight loss study involving FBT. The same random coefficient models with two covariance structures that we described earlier with the same IRGT design will be applied here with the modification that we will focus on the two baseline measures of current interest (parental inconsistency and environmental enrichment) as covariates. Because we anticipate that the efficacy of the intervention may be influenced by these measures, we will also evaluate interaction terms between group assignment and both our parental inconsistency and environmental enrichment measures. The analyses will be performed separately in both participating children and parents.

D. Analysis of Exploratory Aim 1

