24. fresh bananas, oranges, pineapple, melons	Yes No	Yes No
25. fresh apples, grapes, celery, lettuce	Yes No	Yes No
26. potatoes, corn on the cob, whole tomato, frozen vegetables	Yes No	Yes No
27. "100% fruit juice"	Yes No	Yes No

For the following electronic devices, please write down the total number in each room that work, regardless of how many functions they have.

If an electronic device has multiple functions, please list each function in the appropriate spot UNLESS it is a DVD/CD player. If it is a DVD/CD player, list it under DVD. However, if you have a stereo that plays CDs, tapes, and the radio, count all three as separate devices.

General room categories are listed at the end for you to add rooms that are specific to your home that may have the following functions (e.g., additional bedrooms, dining room, etc.). BR stands for Bedroom.

Electronics	Kitchen	Living Room	Parent's BR	Child's BR	BR #3:	BR #4:	Other Room:
28. TVs							
29. VCR (not portable)							
30. DVD player (not portable)							
31. Digital TV recorders (e.g., TiVo, ReplayTV)							
32. Radio (not portable) can include alarm clock							
33. CD player (not portable)							
34. Tape Player (not portable)							
35. Desktop computer with internet access							
36. Desktop computer without internet access							
37. Video game player (e.g., Playstation, xbox)							
38. Telephone (non-cell phone)							
39. Portable CD player							
40. Portable Tape Player							
41. Portable Radio Player							
42. Portable MP3 player (ex: iPod)							
43. Portable DVD player							
44. Hand held videogame player (e.g., Game boy, Sony PSP etc.)							
45. Laptop or portable computer							
Total number of electronics in each room:							

Which of the following things are available and in useable condition in your home or yard/common area? Do not include things that are buried in boxes (except toy boxes), buried in a closet, or in storage. Please circle either “Not Available” or “Available,” and then indicate whether your child commonly uses the item(s) If any of the items listed for each question is available, circle available.
						
Activities	Not Available	Available	If available, does your child commonly use this item?			
46. bike	0	1	Yes No N/A			
47. basketball hoop (includes child size or adult size)	0	1	Yes No N/A			
48. jump rope	0	1	Yes No N/A			
49. sports equipment (e.g., balls, racquets, bats, sticks)	0	1	Yes No N/A			

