50. swimming pool (including kiddie pool)	0	1	Yes No N/A			
51. roller skates, skateboard, scooter	0	1	Yes No N/A			
52. fixed play equipment (e.g., swing set, play house, jungle gym)	0	1	Yes No N/A			
53. home aerobic equipment (e.g., treadmill, cycle, cross trainer, stepper, rower, workout video or audiotapes)	0	1	Yes No N/A			
54. weight lifting equipment, toning devices (e.g., free weights, pull up bars, exercise balls, ankle weights, etc.)	0	1	Yes No N/A			
55. water or snow equipment (e.g., skis, skates, canoe, row boat, surf board, boogie board, windsurf board, slip-n-slide, etc.)	0	1	Yes No N/A			
56. yoga/exercise mats	0	1	Yes No N/A			
57. exercise, play, or recreation room	0	1	Yes No N/A			

58. trampoline	0	1	Yes No N/A
----------------	---	---	------------------

59. How many books are in the home that are approximately at your child's reading level and that he/she has access to? (please check all that apply)						
 0 books  1 - 10 books  11 - 20 books  21 - 30 books  31 - 40 books  41 or more						
Books	Never	Rarely	Sometimes	Often	Very Often	Always
60. How often does a parent or caregiver in the home read to your child?						
61. How often does your child read for pleasure?						
62. How often does your family receive magazines and/or newspapers?						
63. How often does a parent or caregiver take your child to a museum?						
64. How often does a parent or caregiver take your child to a show or performance?						
65. Are there any musical instruments in the home that your child has access to?	Yes	No				
66. Does your child receive lessons for singing or playing a musical instrument?	Yes	No				
67. Does your child engage in any other regular hobbies or activities? If YES, please specify: _____	Yes	No				

Scoring for Environmental Enrichment:

1-23: Land-Use Mix Diversity

Responses (item scoring):

1-5 min (5) 6-10 min (4) 11-20 min (3) 20-30 min (2) 30+ min (1) don't know (1)

Additional scoring: Tally the number of items ≤20-minute walk (either a '3', '4' or '5' response) and call this 'tally of close facilities'

24-27: Fruit and Vegetable

Each food item can be given a total of up to 5 points (range: 0-5). Points are given – then summed to get the total points for that food item – based on (a) presence in the home, (b) the child being able to immediately eat the food, and (c) amount present:

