"In home?" – Yes=1, No=0

"Child can immediately eat?" – Yes=1, No=0

"How much is there?" – A little=1, Some=2, A lot=3

28-45: Electronic Equipment

OVERALL TOTAL = The total number of electronics in the household: Sum the "total" row for all rooms (i.e., kitchen, living room, etc.), including the total for "in house (not always in 1 room)." If "total" for a given room is blank, code that room as 0.

46-58: Physical Activity

Each physical activity item can be given a total of 0, 1, or 2 points. Points are given – then summed to get the total points for that physical activity equipment item – based on availability and whether the child uses the item:

“Which of the following things are available and in usable condition in your home or yard/common area?”

Not available = 0, Available = 1

“If available, does your child commonly use this item?”

Yes = 1

No = 0

N/A = 0

Total score = sum of physical activity item points (items 41-53)

59-67: Cognitive Stimulation

A total of 0-28 points may be awarded based on the presence of cognitively-stimulating items in the child’s home. These questions are scored on different scales, as follows:

Item 59 (“How many books...”)

0 books = 0

1-10 books = 1

11-20 books = 2

21-30 books = 3

31-40 books = 4

41 or more books = 5

Items 60 – 64 (“How often does a parent...”)

Never = 0

Rarely = 1

Sometimes = 2

Often = 3

Very Often = 4

Items 65 – 67

Yes = 1

No = 0

Total score = sum of points awarded for items 59-67

Summary Score for Environmental Enrichment Questionnaire: Sum all subscales to create a global score of non-snack food reinforcers available to the child.

Attitudes toward Evidence-Based Treatment. (Exploratory Aim)

The following questions ask about your feelings about using new types of therapy, interventions, or treatments. Manualized therapy, treatment, or intervention refers to any intervention that has specific guidelines and/or components that are outlined in a manual and/or that are to be followed in a structured or predetermined way. **Indicate the extent to which you agree with each item using the scale shown below.**

	0 Not at all	1 To a slight extent	3 To a moderate extent	4 To a great extent	5 To a very great extent
1. I like to use new types of therapy/interventions to help my clients.					
2. I am willing to try new types of therapy/interventions, even if I have to follow a treatment manual.					
3. I know better than academic researchers how to care for my clients.					

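### The environmental-enrichment scoring key sums the wrong item numbers for activity equipment and gives no value to the response Always, so the Secondary Aim 4 predictor is not properly defined

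*Combined protocol and SAP*

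**What the plan says.** The Statistical Considerations chapter (Analysis of Secondary Aim 4) studies baseline predictors of outcome, "with the measures of interest being parental inconsistency and environmental enrichment". Both measures enter the random coefficient models as covariates, and each is also tested for interaction with group assignment. The hypothesis is that FBT, compared with UC, benefits families with more parental inconsistency and less enriched environments.

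The enrichment score is defined only in Appendix C, under Scoring for Environmental Enrichment. (The questionnaire there is labelled Secondary Aim 3. The current analysis plan numbers this aim as Secondary Aim 4, and that number is used here.)

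- The electronics subscale is headed "28-45: Electronic Equipment".
- The next subscale is headed "46-58: Physical Activity". Each item earns 0, 1 or 2 points: one for being available and one for common use by the child. The total is then given as "Total score = sum of physical activity item points (items 41-53").
- For cognitive stimulation (items 59 to 67), "A total of 0-28 points may be awarded". Item 59 runs from 0 to 5, items 60 to 64 run from Never at 0 to Very Often at 4, and items 65 to 67 are scored 0 or 1.
- A global score adds all the subscales.

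**The concern.** The two defects differ in kind.

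The first is a contradiction inside one subscale. The heading and the summing rule beneath it name different items. On the form, item 41 is "41. Portable Radio Player" and item 45 is "45. Laptop or portable computer", both in the electronics table. Item 54 ("54. weight lifting equipment, toning devices") belongs to the activity table but lies outside the stated sum.

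The second is a gap. On the form, the response columns for items 60 to 64 run from Never to Always, six in all. The key stops at the fifth. It has no rule for a response without a score; its only instruction about blanks concerns room totals in the electronics subscale.

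At stake is the enrichment term in Aim 4. Dropping activity items makes that subscale a poorer measure of what it is meant to capture. An unscored Always either removes a family from the analysis, selectively by its answer, or, if coded as 0, gives it the same score as a family answering Never.

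**Working it through.** The inputs are the item numbers on the Environmental Enrichment form and the point values in its key, all in Appendix C.

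**Activity subscale**

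1. Items under the subscale heading: 46 to 58, so 58 − 46 + 1 = 13 items. The form agrees: item 46 is the first activity item and item 58 the last.
2. Items in the summing rule: 41 to 53, so 53 − 41 + 1 = 13 items.
3. Overlap of the rule with electronics (28 to 45): items 41, 42, 43, 44 and 45, which is 5 items.
4. Overlap of the rule with activity (46 to 58): items 46 to 53, which is 8 items.
5. Activity items left out: 54, 55, 56, 57 and 58, which is 5 items.
6. Maximum over all activity items: 13 × 2 = 26.
7. Maximum over the activity items inside the stated range: 8 × 2 = 16.
8. Largest possible loss: 26 − 16 = 10 points. A family loses all 10 only if it owns, and the child commonly uses, every one of items 54 to 58.

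The two ranges have equal length and are offset by exactly five at each end (46 − 41 = 5 and 58 − 53 = 5). That pattern fits item numbers left over from a different numbering.

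**Cognitive-stimulation subscale**

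1. The plan's own range, reproduced: 5 (item 59) + 5 × 4 (items 60 to 64) + 3 × 1 (items 65 to 67) = 28. This matches the stated 0 to 28, so the key was built with 4 as the top score for items 60 to 64. The missing value is not a line lost from the text.
2. Points resting on items 60 to 64: 5 × 4 = 20 of 28.
3. If Always were coded 0, a family answering Always to all five could reach at most 5 + 0 + 3 = 8.
4. If Always were scored 5 (an assumption), the maximum would be 5 + 5 × 5 + 3 = 33.
5. If Always were scored 4, together with Very Often (also an assumption), the maximum would stay at 28.

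The documents do not choose between steps 3, 4 and 5.

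**The case against.** The strongest reply is that the range error is a slip that a careful scorer would catch. The heading, the form and the point rules all indicate 46 to 58, and only the bracketed numbers disagree. Items 41 to 45 have neither an availability field nor a use field, so the activity rule cannot be applied to them. No scoring program is included, so nothing shows that 41 to 53 was ever used. This stands, and it makes the first defect a contradiction to correct rather than evidence of a wrong analysis. It does not help with Always, because no careful reading supplies a value that the documents do not contain.

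A second reply is that the Aim 4 text does not say whether the global score or separate subscales enter the model. It names questions from a home-environment scale and a land-use subscale. The land-use items (1 to 23) are untouched by either defect. This also stands, and it limits the reach of the point.

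Two stronger readings are tempting and should be set aside:

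- A reader might infer that device counts for items 41 to 45 enter the activity total without limit and are then counted twice in the global score. The key does not say so. Its rule sums activity points of 0 to 2, which those items lack, and electronics are scored from room totals.
- A reader might infer that the unscored response lies at the end of the scale that the hypothesis names. It does not: the hypothesis names less enriched environments, and Always is the opposite end. The gap still matters because an interaction term uses the whole range.

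**Conclusion.** Both defects are real and can be checked against the form. The written activity total omits five of thirteen activity items, a loss of up to 10 of 26 points, and names five items that have no activity points. Always has no score on five items that carry up to 20 of the 28 cognitive points.

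The consequence is conditional. It reaches Secondary Aim 4 if the key is followed as written, or if Always is left unscored, and if the activity subscale, the cognitive subscale or the global score enters the model. The 10 and 20 points are maxima for a single family. How many families chose Always, or own items 54 to 58, is not in the documents, so no effect on the interaction estimate can be given. The primary outcome is unaffected. Correction is still warranted, because this appendix is the only definition of a score used as a prespecified predictor and effect modifier.

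**What to change.** 1. In the activity total, replace items 41 to 53 with items 46 to 58.
2. Before the Aim 4 analysis, reconcile the form and the key for items 60 to 64 and state one value for Always. Two options are 5, which changes the subscale range to 0 to 33, and 4 combined with Very Often, which keeps 0 to 28. The documents do not determine the choice, so the study team should record it with its reason.
3. Recompute the two subscales and the global score from the stored item responses.
4. State in the Aim 4 section which enrichment score, global or by subscale, enters the model.

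The cost is a few lines of wording in the key and the analysis plan, and one rescoring run. No new data are needed.

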To account for differences in the frequency of participant contact between the two study groups, blinded measurement staff will systematically assess for AEs in both the intervention and control groups through use of a standardized questionnaire (see MOP) that is administered at each major assessment time point. If any items are endorsed on the questionnaire, the blinded measurement staff will gather additional information and, if necessary, follow the steps for recording and reporting adverse events outlined below and in section **IX.E**. AEs uncovered in the course of treatment will also be subject to the procedures below. Combining between visit and at visit AEs will result in an alternative count that the DSMB requested. This alternative count will be comprised of all AEs, whether reported at or between visits. Blinded coaches will be unaware if an AE was reported between visits, and any duplicates will be removed by an unblinded reviewer (*DSMB Approval, 12.16.2020*)

All AEs, including those not meeting the criteria for SAEs, will be captured on an Adverse Event Form or Serious Adverse Event Form (see **Appendix D**), which must be approved of and signed by the clinical site PI. Information to be collected includes event description, time of onset (and offset if applicable), assessment of severity, relationship to study treatment, expectedness, actions taken,

and outcome of the event. Additionally, all SAEs will require categorization (e.g., death, hospitalization, permanent impairment, etc.) and documentation of any interventions implemented in response to the event.

All AEs occurring during a participant's study participation must be documented appropriately regardless of relationship. All AEs will be followed by the DSMB to adequate resolution and will be recorded in the data collection system. Any medical condition that is present at the time that the participant is screened will be considered as baseline and not reported as an AE. However, if the study participant's condition deteriorates at any time during the study, it will be recorded as an AE. Changes in the severity of an AE will be documented to allow for an assessment of the duration of the event at each level of severity. AEs characterized as intermittent require documentation of onset and duration of each episode.

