The clinical site PIs will record all reportable events with start dates occurring any time after informed consent is obtained until 7 (for non-serious AEs) or 30 days (for SAEs) after the last day of study participation. Events will be followed by the DSMB for outcome information until resolution or stabilization.

It is important to note that in previous similar clinical trials in the PIs' respective laboratories, the procedures outlined above have been used to protect against and minimize potential risks to participants, and they have proved effective in preventing emotional and physical complaints as well as adverse events.

Due to the fluid situation of COVID-19, 3 additional questions have been added to the AE questionnaire. Asking these questions could give us data on the effects of the pandemic and could help explain changes in FBT attendance and assessment retention.

- i. Do you have a positive COVID-19 test?
- ii. Did you have exposure to someone with a known positive COVID-19 test?
- iii. Did you need to get tested for COVID-19?

(emergency status implemented 3.16.2020, DSMB approval, 5.7.2020)

Adverse Event Reporting Procedures

Upon initial receipt of information, all fatal or life-threatening suspected serious adverse events will be immediately reported to the IRB of Record, internal IRBs, NHLBI, SMC, and DCC via [name] and the clinical site PIs. All non-fatal, non-life-threatening suspected SAEs will be reported within 15 calendar days to the IRB of Record, internal IRBs, NHLBI, SMC, and DCC via [name] and the clinical site PIs. Any unanticipated problems that do not classify as SAEs will be reported within 14 days of the investigator becoming aware of the problem to the IRB of Record, internal IRBs, NHLBI, SMC, and DCC via [name] and the clinical site PIs. All UPs will also be reported within 30 days of the IRB's receipt of information to the Office for Human Research Protection via the IRB. Non-serious adverse events will be documented in the study database following their occurrence and will be reported annually to the IRB of Record and internal IRBs via [name] and the clinical site PIs. See Table 6 for a detailed outline of reporting timelines.

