In addition to the existing procedures referenced above, the SMC recommends that as soon as child mental health SAEs are reported, to a coach or a PLAN staff designee verbally informs the participants' primary care provider and/or pediatric office staff designee with the description of the SAE, date, and referral so that they may follow-up according to their office procedure. Specifically, if a child enrolled in the study reports self-injury, a suicide attempt, or harm to others, then this will be addressed as a SAE and reported verbally to the pediatrician. The event will be reported by the individual with the most amount of information within 24 business hours of learning about the event. If a medical, behavioral, or mental health intervention is **deemed necessary to address this event, it is the pediatrician's responsibility to follow up with their patient to ensure appropriate care is provided**. Before this procedure goes into effect, the PLAN coach will communicate this plan with each pediatric practice to develop a practice-specific protocol with who to contact and how. In the event that a coach is unsure about the severity of the child mental health AE, they will collaborate with the local-site PI to determine the severity of the event and whether or not it should be reported to the pediatric office. All other mental health AEs will not be reported to the pediatrician, but will be reported to the IRB and DSMB as part of normal reporting procedures (***DSMB approved protocol addenda, 11.18.19***).

If a parent becomes pregnant, the PLAN coach will notify the clinical site PI and all weight loss treatments will be stopped. The family's continuation in the study will be limited to the child, siblings and non-participating parent if enrolled. The DCC, DSMB, and IRBs will be notified through

AE reports and a standard form for excluding participants from further data collection and treatment. Please see **Table 10** below for further details regarding AE reporting.

TABLE 10. Adverse Event Reporting Guidelines

What Event is Reported	When is Event Reported	By Whom	To Whom
Fatal or life-threatening unexpected, suspected serious adverse event	Immediately upon initial receipt of information	Contact PI	
 • IRB of Record • NHLBI • SMC • DCC • All PIs and Co-Is
		Clinical Site PIs	
 • Internal IRBs

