observed SAEs and a given defined acceptable SAE rate. For example, suppose we define 2% as the maximum acceptable SAE rate. Then **Table 11** indicates that if the third SAE occurs in fewer than 41 intervention group subjects, then the guideline will have been exceeded because the SAE rate is greater than the acceptable 2% value with 95% certainty.

TABLE 11. MAXIMUM ACCEPTABLE SAE RATES

Number of Observed SAEs	Maximum Acceptable SAE Rate				
	2%	4%	6%	8%	10%
2	18	9	6	4	3
3	41	21	14	10	8
4	69	34	23	17	14
5	99	50	33	25	20

Several points about the above discussion are worth mentioning. First, we have used the term “guideline” instead of “rule” because we view the decision making process as one in which the guideline triggers a multifaceted discussion with the DSMB of whether the study should be stopped or modified because of the observed SAE rate. We do not view reaching the stopping boundary as a rule that should automatically lead to the termination of the study. Second, the rule will be applied both to parents and children separately. Third, we propose setting 2% as the maximum acceptable SAE rate because of the low anticipated SAE rate in this study.

At each DSMB meeting, recruitment and retention data will be presented to the DSMB. If recruitment is less than 90% of the target or if retention is less than 80% among randomized subjects, study investigators will present proposals for improvements in each of these two domains. Note that we use an 80% figure for retention because the original power computations had assumed a 20% dropout rate. Thus, an 80% retention rate is not an indication of reduced statistical power. If under performance by these definitions in either of these domains is present, the DCC will perform conditional power computations based on various scenarios regarding the degree of improvement that can be anticipated in recruitment and/or retention. As was the case in our original power computations, we will adopt the conservative approach of assuming that study dropouts provide no data. We propose that early termination be considered if the conditional power under the recruitment/retention scenarios the DSMB views as most realistic is less than 50%. Any final decision about recommending early termination will consider factors such as the impact of early stopping on information about secondary endpoints and covariate effects. It will also consider the adequacy of the measures that are proposed to increase recruitment and retention.

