1. Strongly Agree
2. Agree
3. Neither Agree or Disagree
4. Disagree
5. Strongly Disagree

The content of FBT is clear.

1. Strongly Agree
2. Agree
3. Neither Agree or Disagree

4. Disagree
5. Strongly Disagree

FBT can be implemented without requiring an extensive training.

1. Strongly Agree
2. Agree
3. Neither Agree or Disagree
4. Disagree
5. Strongly Disagree

FBT can be adapted or modified to suit the needs of the interventionist.

1. Strongly Agree
2. Agree
3. Neither Agree or Disagree
4. Disagree
5. Strongly Disagree

The benefits of using FBT with my clients are obvious/visible.

1. Strongly Agree
2. Agree
3. Neither Agree or Disagree
4. Disagree
5. Strongly Disagree

The evidence regarding the impact of FBT is available.

1. Strongly Agree
2. Agree
3. Neither Agree or Disagree
4. Disagree
5. Strongly Disagree

The content of FBT is relevant to my work as a clinical treatment provider.

1. Strongly Agree
2. Agree
3. Neither Agree or Disagree
4. Disagree
5. Strongly Disagree

Coach consent

Please upload the .pdf file of the signed Coach consent.

Indicate yes or no that Coach consent is uploaded.

[figure not shown]
- No

- Yes

Why is the coach consent not uploaded? _____

D. Additional Forms

Figure 1. Study Flow Chart

PLAN Adverse Event Questionnaire

During the time since your last visit on (*insert date of last major assessment*), have you or your child:

1. Been hospitalized overnight?

YES NO

2. Been to the emergency room or an urgent care clinic?

YES NO

3. Been treated by a medical provider for illness or injury?

YES NO

4. Had any injuries (e.g., sprained ankle or broken bone)?

YES NO

5. Started any new medications or receive a change in dosage of a current medication?

YES NO

6. Experience increased symptoms of a current illness or injury (If applicable)?

YES NO

7. Seen a new counselor, psychologist, or psychiatrist?

YES NO

8. Gone long periods (8 waking hours or more) without eating to control your weight?

YES NO

9. Felt like you have lost control over your eating?

YES NO

10. Thrown up after eating?

YES NO

11. Taken laxatives or diet pills?

YES NO

12. Felt particularly nervous, worried, or anxious?

YES NO

13. Felt very sad or down? Or lost interest in things that you normally enjoy doing?

YES NO

(This change was made on 5.23.18 prior to review and approval by the DSMB, DSMB approved protocol addenda on 11.2.18)

ADVERSE EVENT FORM

The Effectiveness of Family-based Weight Loss Treatment Implemented in Primary Care

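### The printed adverse event questionnaire has no direct item on self-injury, suicidality or harm to others and no separate parent and child answers, and the plan does not say which event count the arms are compared on

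*Combined protocol and SAP*

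**What the plan says.** The section Adverse Event Assessment and Tracking gives the questionnaire its purpose: "To account for differences in the frequency of participant contact between the two study groups, blinded measurement staff will systematically assess for AEs" in both groups, at each major assessment. If any item is endorsed, the blinded staff ask for more detail and, where needed, record the event. Events found during treatment are recorded too. Adding them to the at-visit events gives a second, alternative count that the DSMB requested.

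Adverse Event Reporting Procedures, in text approved by the DSMB on 18 November 2019, says that "if a child enrolled in the study reports self-injury, a suicide attempt, or harm to others, then this will be addressed as a SAE" and is to be told to the pediatrician. Table 8 lists suicidal ideation as a possibly related event that is not marked as expected.

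The 13-item form is in Appendix D, and Adverse Event Reporting Procedures points there for it. Its last marked change is dated 23 May 2018. The stem asks "have you or your child" and each item takes one YES or NO. The mental-health items are 12 (nervous, worried or anxious) and 13: "Felt very sad or down? Or lost interest in things that you normally enjoy doing".

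The Safety Monitoring Committee subsection and Adverse Event Reporting Procedures both have the data coordinating center report monthly on whether AE and SAE rates differ between the groups. Under Study Halting Rules, the SAE guideline concerns the intervention group, and "the rule will be applied both to parents and children separately".

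**The concern.** A questionnaire can even out detection between arms only for the events it asks about. The child events that the protocol singles out as serious are not asked about directly. An event that no one asks about is recorded only if an indirect item leads to it or the family volunteers it, and FBT families have many more occasions to volunteer.

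Two things are at stake. First, a between-arm comparison that includes volunteered reports could make FBT look less safe through detection alone. Second, the notice to the pediatrician depends on the event being reported, so an event in a UC child that no one asks about may be neither counted nor passed on. The joint answer adds a smaller problem: the form itself does not show whether a YES refers to the parent or the child, although the SAE guideline needs them apart.

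**Working it through.** **1. Items against events.** Reading all 13 items:

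| Event | Items that could lead to it | Left without a prompt |
|---|---|---|
| Self-injury or suicide attempt that led to care | 1 ("Been hospitalized overnight"), 2 (emergency or urgent care), 3 (treated by a provider), 5 (new or changed medication), 7 (new counselor, psychologist or psychiatrist) | Little |
| Self-injury or attempt without care | 4 (any injury; the examples given suggest accidents), 12 and 13 if the mood is disclosed | Events not thought of as an injury, with no low mood reported |
| Suicidal thoughts | 5 or 7 if treated; 12, 13 | Thoughts with no care and no disclosed mood |
| Harm to others | 5 or 7 only if it led to treatment | Most |

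**2. The nearest figures in the plan.** The point rests on no stated number. The related figures are the SAE boundaries in Table 11. Taking the largest N whose one-sided binomial tail is at most 0.05, all 20 cells reproduce. For 3 SAEs at a 2% acceptable rate the tail is 0.0486 at N = 41 and 0.0515 at N = 42, matching the stated 41. The boundaries are sound. What under-detection affects is the number of SAEs fed into them.

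**3. Opportunity to report.** Participant Timeline gives four assessments after baseline in both arms and 26 to 96 FBT sessions. The lower figure agrees with Table 6: 8 + 8 + 6 + 4 = 26.
- UC: 4 scheduled contacts.
- FBT: 26 + 4 = 30 to 96 + 4 = 100.
- Ratio: 30/4 = 7.5 to 100/4 = 25.

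**4. Illustration on assumed values.** The documents give no detection rates, so these are assumptions:
- n = 528/2 = 264 children per arm
- equal true two-year risk p = 2%, so 264 × 0.02 = 5.28 true events per arm
- questionnaire sensitivity q = 0.3 to 0.8, the same in both arms
- coach detection c of the events the questionnaire misses = 0.5 to 0.9 in FBT, and none between visits in UC

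UC recorded = n·p·q. FBT recorded, combined count = n·p·[q + (1 − q)c]. Ratio = 1 + (1 − q)c/q, which does not depend on p.

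| q | c | UC | FBT | Ratio |
|---|---|---|---|---|
| 0.3 | 0.5 | 1.58 | 3.43 | 2.17 |
| 0.3 | 0.9 | 1.58 | 4.91 | 3.10 |
| 0.5 | 0.5 | 2.64 | 3.96 | 1.50 |
| 0.5 | 0.9 | 2.64 | 5.02 | 1.90 |
| 0.8 | 0.5 | 4.22 | 4.75 | 1.12 |
| 0.8 | 0.9 | 4.22 | 5.17 | 1.22 |

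On the at-visit count alone the ratio is q/q = 1.0, but 1 − q, or 20% to 70% of events, is missed in each arm.

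**The case against.** The strongest reply is that the plan already separates the two counts. Blinded staff put the same questions to both arms, so the at-visit count does not depend on coach contact, and the count that adds between-visit reports is labelled as an alternative. This stands. A reader might infer that the arm comparison simply reflects coach contact; the documents do not support that. What remains is that neither section describing the monthly comparison says which count it uses.

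Second, the indirect items with follow-up reach further than care alone. Item 4 requires no treatment and item 13 asks about mood. This stands for many events, though not for harm to others or for events the family does not link to an item.

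Third, a YES is a screening step. The SAE form carries participant ID, sex and age, the AE form asks about the participant, and Table 4 lists both parent and child as examinees. Attribution is therefore not necessarily lost. A reader might go on to calculate lost power for item-level child rates, but the plan proposes no such analysis.

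Fourth, Adverse Event Assessment and Tracking also refers to the Manual of Procedures, which is not among the documents, so the form in use may differ from the print. That section says "3 additional questions have been added to the AE questionnaire" and lists them, yet they are not on the Appendix D form. This limits the finding to the printed form; the COVID-19 gap itself is clerical. Nor does the unqualified wording on vomiting and laxatives matter much: follow-up decides what is recorded, and Table 9 already classes brief vomiting as expected and unrelated.

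**Conclusion.** The point holds in moderate form. On the printed questionnaire it is plain that no item asks directly about self-injury, suicide attempt or thoughts, or harm to others, and that parent and child share one answer. The form's last marked change precedes the rule that made these child events SAEs, and the print shows no later alignment.

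Two consequences follow. The at-visit count will miss some of these events in both arms. Any count that adds between-visit reports is likely to detect more in FBT. The ratio of about 1.1 to 3.1 shows how far this could go with no true difference, but it rests wholly on the assumed q and c. Its low end is close to no distortion, and any volunteering by UC families between visits, for instance in scheduling calls, would shrink it further.

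Balance in the at-visit count also assumes the same blinded administration in both arms. Adverse Event Reporting Procedures reserves the questionnaire for blinded measurement staff after measurement, whereas Step 1 of the Remote assessments Protocol places it in the coach's scheduling call. These passages must be reconciled. No sample size, power or alpha figure for the primary analysis changes.

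**What to change.** - Add one direct item on self-injury, suicide attempt or thoughts, and harm to others, asked by blinded staff in both arms after measurement and routed to the existing steps in Adverse Event Reporting Procedures. Direct questioning has a precedent in the study: the parent's screening PHQ asks about thoughts of death or self-harm.
- Give separate Parent and Child answers on the form.
- State that the between-arm comparison uses the at-visit count. Report the combined count beside it, with the caveat that ascertainment was unequal.

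The cost is one form revision, about a minute per visit, and a break in the series at the change date, which reports must mark. Assessors need the existing crisis procedure to hand. The benefit reaches only the remaining assessments. With randomization running to 15 August 2019, the last target dates are 15 August 2020 for 12 months, 15 February 2021 for 18 months and 15 August 2021 for 24 months. A change made after the December 2020 approvals would therefore reach only late 18-month and 24-month visits. Stating which count is compared takes only a sentence and applies to the whole trial.
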